10.17 Timed 25-Foot Walk

The T25FW is the time needed for a patient to walk 25-feet and will be performed at Day 1 H0 and D21 of each treatment period. The test consists of two trials separated by a 5-minute rest period. The maximum duration of each trial is set to 3 minutes (180 seconds).

The average T25FW (expressed in seconds) will be derived for each patient as the average of the two trials..

If a patient only performs 1 of the 2 trials at a given analysis day, the unperformed trial will be imputed using the highest T25FW (180 seconds) to perform the main analysis. An exploratory analysis will also be conducted without imputing unperformed trial as missing thus, leading to a missing average T25FW.

If a patient is not using the same device or is introducing a device within a given treatment period, the average T25FW will be set to missing.

The change and percentage change from baseline will then be calculated (as respectively described in [Section 10.3](#) and in [Section 10.4](#)).

The percentage change from baseline will be categorized as $\leq -20\%$ and $> -20\%$ to assess respectively $\geq 20\%$ improvement (as response) and $< 20\%$ improvement (as non-response) using imputed T25FW (as described above).

Missing average T25FW will be considered as not having met the improvement criteria (imputed as failure).

10.18 11-point Numerical Rating Scale Score (NRS-Spasticity Score)

The 7-day average 11-point NRS spasticity score will be derived for each patient as the mean NRS-spasticity score recorded in the eDiary during the last 7 days preceding Period 1 Day 1 H0 (Baseline), and Day 15 and D21 of each treatment period as follows:

Sum of the NRS spasticity scores during the 7 – day period

Number of days in which the daily diary was completed during the 7 – day period

For each assessment timepoint, the 7-day average 11-point NRS-spasticity score will be set to missing if scores are missing for 4 days or more in total or for 3 consecutive days within each 7-day period.

In case of the diary data are available but the visit does not take place the target visit date will be used.

On-treatment / off-treatment assessment

A 7-day average 11-point NRS spasticity score will be considered on-treatment if derived using only post baseline daily scores collected on or before the date of IMP discontinuation and will be considered off-treatment otherwise.

In case of IMP discontinuation, if possible with regards to missing data rule specified just above, the 7-day average 11-point NRS spasticity score considered on-treatment will also be derived using only post-baseline scores collected on or before the date of IMP discontinuation.

The change from baseline will then be calculated (as respectively described in [Section 10.3](#)).

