12.5.2.3.2 Response Analyses Based on LLMT-6

The reduction from baseline to D21 of respectively $\geq 20\%$, $\geq 30\%$, $\geq 40\%$, $\geq 50\%$ (as described in [Section 10.16](#)) will be analyzed using a logistic regression applied to crossover design using a generalized estimating equation (GEE). The models will be analyzed using the SAS® GLIMMIX procedure with a logit link function and a binary distribution. The marginal log likelihood will be approximated with an adaptive Gauss-Hermite quadrature (obtained using the EMPIRICAL option of the SAS® GLIMMIX procedure) using a likelihood-based sandwich estimator.

The preferred model will include a period level LLMT6 baseline covariate, treatment arm, treatment period, and treatment sequence as fixed effect.

An unstructured covariance will be used to model the residual errors between LLMT-6 scores within the same patient across period. The denominator degrees of freedom will be calculated according to the Kenward-Roger method (e.g. KR2, 2009 version).

This model will provide, for each response analysis, at D21, the estimate of the odds ratios (OR) representing the odds in nabiximols treatment arm versus placebo treatment arm and corresponding 95% CI and nominal p-value. These parameters will be summarized by treatment arm along with number of responders and associated crude response rates.

If less than 5 patients in either treatment arm are considered as responders, only descriptive statistics will be conducted presenting the number and percentage of responders by treatment arm.

In case of non-convergence, appropriate model will be applied.

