12.5.5.1 Timed 25-Foot Walk (T25FW)

A decrease in average time to complete the two trials will show an improvement.

The difference between treatment arms in the change from baseline to D21 in average 25-foot walk time (as defined in [Section 10.17](#)) will be analyzed using the same LME model for crossover data as the one used for the primary analysis of the primary efficacy endpoint (as described in [Section 12.5.2.1.8](#)). As a sensitivity analysis, the same analysis will be repeated using non-imputed average 25-foot walk times (as defined in [Section 10.17](#)).

If model diagnostics suggests that the residuals are not normally distributed a non-parametric analysis will be conducted.

A $\geq 20\%$ reduction from baseline to D21 of in average time (as described in [Section 10.17](#)) will be analyzed using a logistic regression applied to crossover design using a GEE (as described in [Section 12.5.2.3.2](#)).

A histogram presenting LS means change from baseline estimates along with their corresponding 95% CI will be provided by treatment arm.

Descriptive statistics for the average T25FW values change from baseline and percentage change from baseline by treatment arm will be provided; as well as a by-patient listing presenting observed and derived variables.

12.5.5.2 11-point Numerical Rating Scale Score (NRS-spasticity score)

The 11-point NRS spasticity scale is composed of 11 items ranging from 0 (no spasticity) to 10 (maximal spasticity) to assess the overall spasticity in patients with MS during the last 24 hours.

The difference between treatment arms in the 7-day average NRS spasticity score over the last 7 day preceding D21 of each period (as defined in [Section 10.18](#)) will be analyzed using a linear mixed model for crossover data using the SAS® GLIMMIX procedure with an identity link function and a normal distribution. The 7-day average NRS spasticity D21 score will be included as the dependent variable. Hence, each patient will contribute two measurements to the model, one for each period of the study.

The preferred model will include period level treatment arm, treatment period, and treatment sequence as fixed effects. Unstructured (UN) covariance structure will be used to model the repeated 7-day average NRS spasticity scores. The denominator degrees of freedom will be calculated according to Kenward-Roger method (e.g., KR2, 2009 version).

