	E2, SUP1 (response analysis)	
Variable: proportion of patients with a 20% decrease from period baseline in average T25FW at D21
 
Population: FAS
 
IES:
 
 Regardless permanent treatment discontinuation Regardless premature study discontinuation Regardless major IPD Regardless COVID-19 impact 
PLS: Odd ratio in nabiximols versus placebo
 
Analysis: OR from logistic regression model for crossover data adjusted on period baseline average T25FW. Single imputation: Missing D21 values are imputed a failure.

	E2, SUP2 (Supplementary without major IPD impact)	
Variable: Change from period baseline in average 25-foot walk time at D21
 
Population: PP analysis set
 
IES:
 
 Regardless permanent treatment discontinuation Regardless premature study discontinuation Without major IPD Regardless COVID-19 impact 
PLS: Mean difference between nabiximols and placebo
 
Analysis: LSMD from CFB linear mixed-effect model for crossover data adjusted on period baseline average T25FW. No imputation under MAR assumption

	E2, SUP3 (Supplementary without COVID-19 impact)	
Variable: Change from period baseline in average 25-foot walk time at D21
 
Population: FAS
 
IES:
 
 Regardless permanent treatment discontinuation Regardless premature study discontinuation Regardless major IPD Without COVID-19 impact. 
PLS: Mean difference between nabiximols and placebo
 
Analysis: LSMD from CFB linear mixed-effect model for crossover data adjusted on period baseline average T25FW. No imputation under MAR assumption

Exploratory Objectives: To evaluate the effect of nabiximols after administration of multiple doses on the following patient-reported outcomes: the 11-point Numerical Rating Scale (NRS) spasticity score, Daily spasm count as well as the MS Spasticity Scale (MSSS-88) total and subdomain scores.

11-point NRS-spasticity score	E3, Primary	Variable: 7-day average NSR spasticity score at D21 Population: FAS IES: Regardless permanent treatment discontinuation Regardless premature study discontinuation Regardless major IPD Regardless COVID-19 impact PLS: Mean difference between nabiximols and placebo Analysis: LSMD from observed value linear mixed-effect model for crossover data. No imputation under MAR assumption

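### Timed 25-Foot Walk: filling one unperformed baseline walk with 180 s scores an unchanged walker (120 s or less) as a responder

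*SAP*

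**What the plan says.** SAP 10.17 takes the visit value as the mean of two walks, each capped at 180 s, measured before dosing on Day 1 and on Day 21 of each period. When one walk is not done on an analysis day, "the unperformed trial will be imputed using the highest T25FW (180 seconds) to perform the main analysis". The rule makes no exception for the baseline day, and the E2 Primary entry in Appendix 14 repeats the fill without one.

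The same section defines response as a fall of at least 20% from period baseline, and the definition ends "improvement (as non-response) using imputed T25FW (as described above". Where no average exists: "Missing average T25FW will be considered as not having met the improvement criteria (imputed as failure".

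SAP 12.5.5.1 says that response "will be analyzed using a logistic regression applied to crossover design using a GEE", by the method of 12.5.2.3.2. Appendix 14 (E2 SUP1) describes the result as "OR from logistic regression model for crossover data adjusted on period baseline average T25FW". Under 12.5.2.3.2 the model results are shown "along with number of responders and associated crude response rates", and "If less than 5 patients in either treatment arm are considered as responders, only descriptive statistics will be conducted".

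For the mean change, 12.5.5.1 adds: "As a sensitivity analysis, the same analysis will be repeated using non-imputed average 25-foot walk times". In that repeat a visit with one walk has a missing average. No counterpart is planned for response.

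**The concern.** A shorter time is better (SAP 12.5.5.1), so 180 s is the worst possible value. Put in at Day 21, it counts against the patient. Put in at baseline, it inflates the starting point, and an ordinary Day 21 result then looks like a large improvement. Patients with incomplete baselines are also treated inconsistently: one with no baseline walk is a failure, while one with a single baseline walk is almost automatically a success.

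At stake are the responder counts and rates for walking, and false changes in the data behind the main walking analysis. LLMT-6 and LLMT-4 do not use this rule.

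**Working it through.** The plan states no figure for this rule, so there is none to reproduce. The check is algebra on its own definitions.

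**Inputs.** Fill 180 s, visit value the mean of two walks, response at −20% or lower (all SAP 10.17); percentage change = 100 × (Day 21 − baseline)/baseline (SAP 10.4); target of 68 completers (SAP 8.2). The documents give no walk times, so t below ranges over assumed values.

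**One baseline walk missing, both Day 21 walks done, patient unchanged at t seconds.** Baseline = (t+180)/2 and Day 21 = t, so the change is 100 × (t−180)/(t+180).

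| t (s) | Filled baseline (s) | Change (s) | Change (%) | Scored as |
|---|---|---|---|---|
| 10 | 95 | −85 | −89.5 | responder |
| 20 | 100 | −80 | −80.0 | responder |
| 60 | 120 | −60 | −50.0 | responder |
| 120 | 150 | −30 | −20.0 | responder |
| 121 | 150.5 | −29.5 | −19.6 | non-responder |

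The cut-off: (t−180)/(t+180) ≤ −0.2 gives 1.2t ≤ 144, so t ≤ 120 s. A patient can even get worse: at t = 10 s, any Day 21 average up to 0.8 × 95 = 76 s is still a response.

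**One walk missing at both visits, performed walks t then x.** Response needs (x+180) ≤ 0.8(t+180), so x ≤ 0.8t − 36. That is impossible when t < 36/0.8 = 45 s. A true 30% gain from 10 s to 7 s scores 187/190 − 1 = −1.6%.

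**One walk missing at Day 21 only.** An unchanged 10 s walker goes from 10 s to 95 s (+850%) and is a failure. This is the conservative direction.

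**Effect on the crude rate.** One false responder among 68 is 1/68 = 1.5 percentage points. Missing averages count as failures and SAP 12.0 bases percentages on the patients in the arm, so patients who cannot walk stay in the denominator. The figure is a ceiling if the Full Analysis Set has at least 68 patients.

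**How likely crude counts are the only output.** Assume a response rate p per arm and 68 patients. P(4 or fewer responders) is 0.747, 0.178 and 0.018 for p = 5%, 10% and 15%. For at least one of two independent arms, 1 − (1−P)² gives 94%, 32% and 4%. The arms hold the same patients, and positive correlation would bring these down towards the single-arm values.

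**Effect on the odds ratio.** I simulated 68 patients with no treatment effect and one baseline fill in the nabiximols period. The model was a logistic GEE with treatment, period, sequence and period baseline, which approximates the planned fit. Assumed median times were 6 to 15 s, between-patient log-SD 0.4 to 0.8 and visit log-SD 0.13 to 0.20. The log odds ratio moves by 0.015 to 0.025 at log-SD 0.4 and by up to 0.10 at 0.8, against a standard error of 0.43 to 0.60. Without baseline adjustment the shift is about 0.08 to 0.13.

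**The case against.** The stakes are small. The endpoint is exploratory, outside the hierarchical test and reported with nominal p-values. The fault needs exactly one missing walk at a period baseline, and nothing in the documents suggests that this will be common. The model adjusts for baseline, a by-patient listing would show the case, and with fewer than 5 responders in an arm no test is run that could be distorted. All of this stands and sets the priority. It does not make the responder classification right, and a listing reveals an error without correcting it.

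Scoring an unperformed Day 21 walk at the maximum is a deliberate penalty, in line with counting missing averages as failures. That also stands: the Day 21 fill is a defensible choice and is not faulted here.

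A reader might go further and infer that a single Day 21 fill overwhelms the mean-change estimate. Under the same kind of assumed walk times, one such fill moves the estimate by 1.2 to 1.3 s at 68 patients, but the standard error rises to about 1.3 to 1.9 s. The shift is about one standard error or less, so the main cost is precision. SAP 12.5.5.1 also plans the non-imputed repeat and a nonparametric analysis if residuals are not normal.

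**Conclusion.** The rule gives a wrong result as written. With one baseline walk missing and both Day 21 walks done, every unchanged walker at 120 s or less is counted as a responder. With one walk missing at each visit, no walker under 45 s at baseline can be a responder. Both results follow from the SAP's definitions, provided the walking-device rule in 10.17 has not already set the average to missing.

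The crude count is wrong by up to one patient per baseline fill, and no non-imputed responder analysis is planned to show it. A false change, −85 s for a 10 s walker, also enters the data for the main change-from-baseline model.

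Two stronger readings are not supported. One is that the odds ratio is materially biased: baseline adjustment absorbs most of the shift when walking times vary moderately between patients, and the remainder is small against the standard error even when they vary widely. The other is that the rule favours nabiximols: a fill can fall in either treatment's period, so the direction cannot be predicted.

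The documents do not say how often a single walk will occur, so the total effect cannot be computed. This is a low-priority correction that could be made.

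**What to change.** In SAP 10.17, and in the E2 Primary and E2 SUP1 entries of Appendix 14:

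- When only one walk is done at a period baseline, use its time as the baseline value. Do not fill baseline with 180 s.
- When only one walk is done at both visits, compare the two performed walks.
- If a penalty for an unperformed Day 21 walk is wanted, apply 180 s at Day 21 only, as a labelled analysis. Using the fill at both visits as a sensitivity analysis would bring the baseline fault back.

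An unchanged walker with one missing baseline walk then scores 0%, and a change from 10 s to 7 s scores −30% with one walk at each visit. The cost is a few sentences and a small change to the derivation, made before unblinding. The performed-walk comparison does not penalise a patient who cannot do the second Day 21 walk; the labelled analysis covers that.

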9.2.10 Vital Signs

As part of the screening procedures at Visit 1, vital signs (systolic and diastolic blood pressure and pulse rate) will first be measured after the patient assumed a supine position for 5 minutes. Vital signs will then be measured within 2 minutes of assuming a standing position in ambulatory patients only. At all subsequent time points, vital sign

measurements will be completed in a sitting position at rest for 5 minutes. Blood pressure should be recorded using the same arm throughout the trial, where possible.

Additional vital signs measurements may be taken during the trial if clinically indicated.

9.2.11 12-Lead Electrocardiogram

A 12-lead ECG will be performed after 5 minutes in a supine position. A physician must review the ECG (annotated, signed, and dated) and any abnormal findings considered to indicate significant medical history or AEs must be recorded appropriately on the eCRF. Additional ECG measurements can be taken at any time during the trial, if clinically indicated.

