9.2.15.4 Timed 25-Foot Walk

The T25FW is a quantitative measure of lower extremity function. A blinded, independent, trained, and certified healthcare professional will perform the T25FW. The same assessor should administer the T25FW test throughout the trial where possible. If ambulatory, the patient will be instructed to begin at one end of a clearly marked 25-foot course. They will be instructed to walk the 25 feet as quickly as possible, but safely, and to not slow down until after they have passed the finish line. The task will be immediately administered a second time following the first trial by having the patient walk back the same distance.

Patients will be permitted to use their customary, nonmotorized assistive device (AD) (cane, walking sticks, walker, and rollator) during the T25FW test. The same AD must be used at each assessment and its use documented in the patient record.

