AE = adverse events; C-SSRS = Columbia-Suicide Severity Rating Scale; ECG = electrocardiogram; IMP = investigational medicinal product; MAS = Modified Ashworth Scale; MS = multiple sclerosis; MSSS-88 = Multiple Sclerosis Spasticity Scale; NRS = Numerical Rating Scale; PK = pharmacokinetics; T25FW = Timed 25-Foot Walk; THC = Δ^9 -tetrahydrocannabinol.

^a A washout period of at least 7 days will separate the 2 treatment periods. Following the final dose of IMP in Treatment Period 1, in the morning of Visit 5 (Day 21), patients will discontinue treatment with IMP for the 7 days prior to Visit 6 (Day 31). During the washout period, patients will continue to take their current MS antispasticity medications without any changes in dose.

^b A comprehensive physical examination, including an assessment of height, will be completed at Screening (Visit 1) only; subsequent physical examinations will be symptom-directed.

^c Serum pregnancy test at Visits 1 and 10; urine pregnancy test at Visits 2 and 6 (predose).

^d On the day before PK blood sampling at Visits 4, 5, 8, and 9, patients will be prompted to record whether they started their morning and evening doses of IMP within 30 minutes of a snack or meal. On the day of PK blood sampling, the exact time and date of PK blood sampling and the time of the patient's snacks and meals should be recorded. See **Section 9.2.12.1** for the PK blood sampling schedule. Please note that more than one PK sample may be collected at distinct time points during a single visit.

^e Patients will record their 11-point NRS spasticity score, spasm count, and use of antispasticity medications in an electronic diary once daily, around the same time each day, preferably in the evening before retiring to sleep, for at least 7 days prior to Visits 2 and 6 and throughout the trial until Visit 9. Investigational medicinal product dosing will be recorded by the patient in an electronic diary from Visits 2 through 9.

^f MAS assessments will occur at Visit 1 (Screening) and at scheduled time points before (Visits 2 and 6 [predose]) and after (Visits 2, 5, 6, and 9 [3 hours \pm 15 minutes postdose]) IMP administration; for Visits in which the morning dose consists of more than 1 spray (Visits 5 and 9), postdose assessments will occur 3 hours \pm 15 minutes after the first spray of the morning dose.

^g Non-ambulatory patients are not expected to perform the T25FW test.

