10.4 Percentage Change from Baseline

Percent CFB will be calculated, where applicable, as:

$$(\text{CFB}/\text{baseline}) * 100.$$

If a baseline value has not been recorded for a parameter, then percent CFB will be missing for that parameter.

If baseline and post baseline are rates the following formula will be used:

$$((\frac{\text{Post baseline score}/\text{count} * \text{baseline duration}}{\text{Baseline score}/\text{count} * \text{post baseline duration}} - 1) * 100)$$

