12.5.5 Exploratory Efficacy Analysis

All exploratory efficacy analyses will be conducted among the full analysis set during the 51-day efficacy randomized period.

If more than 20% of patients from FAS are excluded in the PP Analysis Set; the analyses may be repeated using the PP analysis set as described in [Section 12.5](#).

The exploratory efficacy analyses based on LLMT-10 are described in [Section 12.5.5](#).

If at least 5 patients have at least one visit where the studied endpoint is impacted by the COVID-19, as assessed by the investigator, the analysis of that endpoint will be repeated excluding the concerned patients as described below:

- For the average 25-foot walk time (as described in [Section 10.2](#) and in [Section 10.17](#)) if during Period 1 and/or Period 2, D21 visit, T25FW trials are impacted by COVID-19,
- For the 7-day average NRS spasticity score (as described in [Section 10.2](#) and in [Section 10.18](#)) if during Period 1 and/or Period 2, Day 15 or D21 visits are impacted by COVID-19 and patient is infected*,
- For the 7-days average daily spasm counts (as described in [Section 10.2](#) and in [Section 10.19](#)) if during Period 1 and/or Period 2, Day 15 or D21 visits are impacted by COVID-19 and patient is infected*,
- For MSSS-88 total and sub-scales scores (as described in [Section 10.20](#)) if during Period 1 and/or Period 2 at D21 Visit MSSS-88 scoring is impacted by COVID-19.

* For eDiary endpoints, impact on COVID-19 is assessed based on information collected on the "Visit COVID-19 Impact" eCRF form. Thus if reason is due to "Caregiver or family member infected with COVID-19" but not to "Patient infected by COVID-19" the assessment will not be discarded.

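### The T25FW responder rule scores patients who cannot walk as failures in both periods, which shrinks the crude response rates and leaves them on a different set of patients from the odds ratio beside them

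*SAP*

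**What the plan says.** - **Who does the test.** Footnote g of the protocol schedule (Appendix 1), repeated in the SAP schedule, reads: "Non-ambulatory patients are not expected to perform the T25FW test". Protocol 9.2.15.4 makes the procedure conditional in the same way: "If ambulatory, the patient will be instructed to begin at one end of a clearly marked 25-foot course".
- **Who can enrol.** Nothing in protocol 6.1 or 6.2 requires a patient to be able to walk. Protocol 9.2.10 allows for patients who cannot: "Vital signs will then be measured within 2 minutes of assuming a standing position in ambulatory patients only".
- **Population.** SAP 12.5.5: "All exploratory efficacy analyses will be conducted among the full analysis set during the 51-day efficacy randomized period". SAP 9.3.2.3 defines the FAS by randomization and at least one dose, with no condition on walking.
- **Response variable.** SAP Appendix 14 (E2, SUP1) defines it as "proportion of patients with a 20% decrease from period baseline in average T25FW at D21".
- **Missing values.** SAP 10.17: "Missing average T25FW will be considered as not having met the improvement criteria (imputed as failure". Appendix 14 says for the same analysis: "Single imputation: Missing D21 values are imputed a failure". SAP 10.4 adds: "If a baseline value has not been recorded for a parameter, then percent CFB will be missing for that parameter".
- **Reporting.** SAP 12.5.5.1 sends the T25FW response to the logistic method of 12.5.2.3.2, which prints responder counts and crude rates by arm next to the odds ratio. Appendix 14 gives period-baseline average T25FW as the model covariate.

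**The concern.** Failure imputation is a reasonable conservative choice when a patient could have been measured and was not. The same rule for LLMT response in SAP 10.16 fits that description, because entry requires a qualifying MAS score and contractures that prevent MAS assessment are an exclusion. The T25FW is different, because the plan itself expects some patients never to have a value. Scoring them as failures adds the same non-informative record to both arms and lowers both reported rates.

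There is also a mismatch inside one table. The failure rule keeps these patients in the crude rates, while the model needs a baseline walk time that they do not have. Rates and odds ratio would then describe different patients, and nothing in the SAP tells the reader so. If fewer than 5 patients respond in either arm, SAP 12.5.2.3.2 drops the model, and the diluted rates become the only responder result.

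**Working it through.** The documents give no T25FW response rate, no share of non-ambulatory patients and no power for this endpoint, so there is no stated figure to reproduce. The check traces the rules and then works out the dilution under stated assumptions.

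**Tracing one non-ambulatory FAS patient**
1. No T25FW at Day 1 predose or Day 21 in either period (schedule footnote g).
2. Percent change is missing (SAP 10.4), so the 20% criterion cannot be met.
3. The average T25FW is missing, which is a failure under SAP 10.17. The narrower wording in Appendix 14 gives the same result, because the Day 21 value is missing too.
4. The 180-second substitution in SAP 10.17 does not help, because it covers only a patient who performs one of the two trials.
5. Result: one failure under nabiximols and one under placebo.

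**Dilution of the crude rates**

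Let q be the share of FAS patients unable to do the test, and p_N and p_P the response rates among those who can.

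- Reported rate = (1 − q) × p + q × 0 = (1 − q) × p
- Reported difference = (1 − q) × (p_N − p_P)
- Reported ratio = p_N / p_P, unchanged

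Both q and the rates are assumptions:

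| q | 30% v 15% in walkers | Difference (points) | 40% v 20% in walkers | Difference (points) |
|---|---|---|---|---|
| 0% | 30% v 15% | 15 | 40% v 20% | 20 |
| 10% | 27% v 13.5% | 13.5 | 36% v 18% | 18 |
| 20% | 24% v 12% | 12 | 32% v 16% | 16 |
| 30% | 21% v 10.5% | 10.5 | 28% v 14% | 14 |
| 40% | 18% v 9% | 9 | 24% v 12% | 12 |

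For example, at q = 20%: 0.80 × 30% = 24%, 0.80 × 15% = 12%, and 0.80 × 15 points = 12 points.

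**What happens to the odds ratio**

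A GEE logistic simulation (20,000 patients, two periods, q = 20%, walker rates 40% v 20%, exchangeable correlation, in statsmodels rather than GLIMMIX) gave:

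- Crude rates over all patients: 32.4% v 15.7%.
- Crude rates among walkers: 40.6% v 19.7%.
- Model with a baseline covariate that is missing for non-walkers: 80% of records kept, odds ratio 2.79. The walkers' crude rates give the same value: (0.406/0.594) / (0.197/0.803) = 2.79.
- Model without the covariate, which is not the planned one: odds ratio 2.57.

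The planned, covariate-adjusted odds ratio is therefore the walkers-only value, while the rates printed beside it include everyone.

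**The case against.** The strongest case against the point has four parts.

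- **The denominator may not be the whole FAS.** SAP 12.0 allows percentages over patients or over patients at risk, and SAP 10.3 computes change only where both values exist. This stands in part. However, at risk is defined for adverse events (SAP 12.7.1) and not for the T25FW, and SAP 10.17 says what happens when the average is missing: it is a failure. No sentence removes non-walkers.
- **There may be few or no such patients.** This stands. The documents show that non-ambulatory patients may enrol, not that any did. A reader might infer that the reported rates mainly describe people who cannot respond. The documents do not support that, and even at an assumed 30% share, 70% of the denominator are walkers.
- **The treatment effect is not distorted.** This largely stands. A reader might infer that the odds ratio is also diluted, for instance from 2.43 (30% v 15%) to 2.32 (24% v 12%). That unadjusted odds ratio is not a planned output, and the planned one drops the patients concerned. A reader might also suspect bias towards one arm, but a patient who fails on both treatments favours neither.
- **The information can be recovered.** Descriptive statistics with the number of non-missing values and a by-patient listing are planned (SAP 12.0, 12.5.5.1). They show how many patients were measured, but they do not correct the printed rates or state which patients the odds ratio covers.

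**Conclusion.** The point holds as a minor one. As written, the failure rule scores any non-ambulatory FAS patient as a non-responder in both periods, so the crude response rates and their difference are multiplied by (1 − q). With assumed walker rates of 30% v 15%, the 15-point difference becomes 13.5, 12 or 10.5 points at q of 10%, 20% or 30%. The direction holds for any q above zero; the size cannot be fixed, because neither q nor the rates are given.

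The statement about the odds ratio assumes a standard fit that omits records with a missing covariate; the SAP describes no imputation of an absent T25FW baseline. On that assumption the defect is one of labelling: two results in one table on different patients.

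This is a supplementary analysis of an exploratory endpoint with nominal p-values. The primary and secondary analyses are unaffected, and the T25FW change-from-baseline analysis does not use the failure rule.

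**What to change.** In SAP 10.17 and Appendix 14 (E2, SUP1):

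- Restrict the T25FW responder analysis, both crude rates and model, to FAS patients with a Period 1 Day 1 predose T25FW.
- Keep failure imputation for their later missing values, including Period 2 values missing after discontinuation in Period 1.
- Report how many FAS patients have no Period 1 baseline T25FW.
- State the number of patient-periods in the crude rates and in the model.

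The condition should be the Period 1 baseline and not each period's own baseline. Under the primary estimand text in SAP Table 9.1-2, no Period 2 data are collected from patients who stop IMP in Period 1. A period-specific condition would remove those walkers from the Period 2 rates and turn dropout from failure into exclusion. Their Period 2 records would still leave the model for want of a Period 2 baseline, which is why both record counts are needed.

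The count to report is of patients without a baseline walk, because the documents do not show that ambulatory status is recorded separately. The cost is one SAP sentence and a table footnote, with no new data. The downside is that the rates then apply only to patients able to do the test at entry, and a patient whose first test was missed for another reason is also left out.
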